## 9.1.1.2 Dose-Limiting Toxicities

DLTs are any of the following toxicities occurring during Cycle 1 and assessed by the investigator as related to study drug (any toxicities considered related to any degree to E7766):

- Clinically significant nonhematologic toxicity ≥ Grade 3 (National Cancer Institute [NCI] Common Terminology Criteria for Adverse Events [CTCAE] v. 5.0), except
  - Grade 3 fatigue <5 days.
  - Asymptomatic Grade 3 or 4 laboratory abnormalities that are corrected within 72 hours.
  - ≥ Grade 3 nausea, vomiting, and diarrhea unless lasting >48 hours despite optimal supportive care.
  - Other AEs that per investigator assessment are not dose limiting nor dose related.
- CTCAE Grade 2 nonhematologic toxicities which, in the opinion of the investigator, require a dose reduction or discontinuation of study drug, or lead to the subject's failure to complete at least 2 out of 3 scheduled injections of E7766 in Cycle 1, or be

Eisai Confidential Page 54 of 138

- considered intolerable for any other reason by the investigator, may be deemed to be dose-limiting if agreed upon by participating investigators and the sponsors.
- Nonhematologic laboratory findings of Grade ≥3 that were ≤ Grade 1 at baseline with the exception of abnormal Grade 3 laboratory values with no clinical significance that resolve within 7 days (this includes electrolyte abnormalities which respond to medical intervention).
- Hematologic toxicity:
  - Grade 4 neutropenia for ≥5 days, or febrile neutropenia.
  - Grade 4 thrombocytopenia, or Grade 3 thrombocytopenia with hemorrhage.
- Any other toxicity assessed as related to E7766 treatment, and which in the opinion of the study investigator(s) and the study medical monitor constitutes a DLT.
- A delay of initiating Cycle 2 of 7 days or more due to toxicity.
- Any death not clearly due to the underlying disease or extraneous causes
- For patients with hepatic metastases, AST or ALT >8×upper limit of normal (ULN), or AST or ALT >5×ULN for ≥14 days.
- For patients with normal ALT and AST and total bilirubin (TBIL) value at baseline: AST or ALT >3.0×ULN combined with TBIL >2.0×ULN without evidence of cholestasis (ALP ≤2×ULN), with no alternative etiology (Hy's law)
- For patients with elevated AST or ALT or TBIL value at baseline: [AST or ALT >2×baseline AND >3.0×ULN] OR [AST or ALT >8.0×ULN], whichever is lower, combined with [TBIL >2×baseline AND >2.0×ULN] without evidence of cholestasis (ALP ≤2×ULN)

A subject should have received at least 2 E7766 injections during the DLT period (Cycle 1) to be considered evaluable for a DLT, unless the subject experienced a treatment-related toxicity preventing more than 1 administration of E7766.

If a subject at a given dose level receives fewer than 2 out of the 3 planned E77766 intratumoral injections during the Induction cycle (ie, the DLT period/Cycle 1) because of E7766-related AEs, the subject should be considered as potentially experiencing a DLT by the Study Safety Committee, composed of investigators and representatives of the sponsor.

A subject experiencing a DLT may continue treatment at a reduced dose if the DLT has resolved and in the opinion of the investigator the subject is benefiting from treatment. In case of recurrence of the DLT at a lower dose, E7766 treatment should be discontinued.

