Target DLT rate at MTD = 25% and its equivalence interval = 20% to 30%, Cohort size = 2 subjects. Display for more than 12 subjects at the current dose is omitted. If the required rules are not available in the table, the decision will follow the rule determined by the improved mTPI design with the same settings above. E = Escalate to the next higher dose, S = Stay at the current dose, D = De-escalate to the next lower dose, U = Current dose is unacceptably toxic (ie, Do not re-enter the current dose).

DLT = dose-limiting toxicity, MTD = maximum tolerated dose, mTPI = modified toxicity probability interval. a: Extra subjects may be added for the lowest dose, for example if the investigators and the sponsor determine that more subjects would be required to adequately evaluate that dose level and it is considered safe to do so.

Subjects will be assigned to a dose level in the order of study entry. There should be at least 7 days between initiating treatment of the first and second subject in each new dose escalation. This would provide enough safety margin in terms of safety evaluation for any acute serious toxicities arising from activation of the immune system, which would generally be expected to occur within the first hours or 1 to 3 days of drug exposure. In cohorts where the dose is de-escalated or re-escalated, a delay in administration between the first subject and subsequent subjects in that cohort is not required if the same or a higher dose level has already been investigated in a previous cohort.

The first E7766 dose administered to the subjects will be 75  $\mu g$  (refer to Section 9.2 for justification of starting dose). The dose of subsequent dose groups will be determined based on the E7766-related AEs that develop in subjects in the prior dose group during the 3 weeks of Cycle 1 (see Table 2). When escalating or de-escalating the dose to the next dose level according to the improved mTPI design, if there is a higher or lower dose level that has been tested previously, subjects should be enrolled to the previously tested dose and Table 2 below shall not apply. In addition, intermediate doses can be further added if necessary based on the safety or PK of the previously tested dose. The addition of new dose levels will be decided based on discussions between the investigators and sponsors during dose escalation meetings.

Eisai Confidential Page 53 of 138

Table 2	Method for Deciding the Dose of the Next Dose Group
---------	---

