# 9.7.4 Other Statistical/Analytical Issues

## 9.7.4.1 Improved Modified Toxicity Probability Interval Design in Dose Escalation Part

The improved mTPI design, which uses a Bayesian statistical framework and a beta-binomial hierarchical model, will be employed to determine the MTD and/or RP2D of E7766.

Decision rules for dose assignment will be based on the improved mTPI design with the target DLT rate of 25% and its equivalence interval (EI) of 20% to 30%, and a set of equal-width intervals as EI below/above EI (ie, below EI: 0% to 10%, 10% to 20%; above

Eisai Confidential Page 107 of 138

EI: 30% to 40%, ..., 90% to 100%). The posterior probabilities of each interval will be calculated with non-informative beta prior distribution Beta (1, 1). The location of the interval with the largest posterior probability—below EI, EI, or above EI—guides the decision for the next dose level to be assigned, ie, Dose Escalation (E), Staying at the current dose (S), or dose De-escalation (D), respectively. This dose assignment rule minimizes the posterior expected penalty in the Bayes' rule under a decision-theoretic framework with the equal prior expected penalties for E, S, and D. The entire dose assignment decision rule can be pre-tabulated as presented in Table 1.

The subject enrollment will be closed when the lowest dose has a >95% posterior probability of being above the target DLT rate of 25% (ie, an unacceptable DLT rate beyond the target DLT rate) or when the RP2D has been determined.

The MTD is defined as the dose with the smallest difference between the target DLT rate of 25% and an estimate of DLT rate at each dose among all the tested doses with a ≤95% posterior probability of being above the target DLT rate of 25%. The isotonically transformed posterior mean under the beta posterior distribution with non-informative beta prior distribution Beta (0.005, 0.005) will be used to determine the estimate of DLT rates at each dose. The pooled adjacent violators algorithm (PAVA) will be used to maintain monotonically the increase of DLT rate with increasing dose level. Late immune-related toxicities occurring after Cycle 1 (DLT period) and up to 90 days after last dose of E7766, will also be used to inform corrections to the MTD and aid selection of the RP2D.

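### For nonhematologic Grade ≥3 events the investigator alone can grant an exemption from the DLT count, while judgement-based additions need agreement, so DLTs can be undercounted

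*Protocol*

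**What the plan says.** Protocol 9.1.1.2 counts Cycle 1 events that are attributed to the drug, with a low threshold: "any toxicities considered related to any degree to E7766". Its first criterion is "Clinically significant nonhematologic toxicity ≥ Grade 3", followed by four exceptions. Three are tied to a grade, a duration or a correction time. The fourth is "Other AEs that per investigator assessment are not dose limiting nor dose related". It names no one but the investigator and asks for no recorded reason. The synopsis repeats it.

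The same section allows two judgement-based additions:

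- A Grade 2 nonhematologic event "may be deemed to be dose-limiting if agreed upon by participating investigators and the sponsors".
- Any other related toxicity counts if both the investigator(s) and the medical monitor consider it a DLT.

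The Study Safety Committee, made up of investigators and sponsor representatives, is asked to consider a possible DLT in one situation only: fewer than 2 of the 3 Cycle 1 injections given because of related AEs.

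The count feeds Protocol Table 1, whose settings are "Target DLT rate at MTD = 25% and its equivalence interval = 20% to 30%, Cohort size = 2 subjects".

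**The concern.** The exemption is partly circular: whether an event is dose limiting is part of the test for leaving it out of the dose-limiting events. The second condition, that the event is not dose related, is also one person's opinion, and a single event in a cohort of 2 offers little evidence on dose-relatedness. It sits awkwardly beside a stem that accepts any degree of relatedness.

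The concurrence needed is unequal. Taking an event out requires one opinion; putting one in by judgement requires at least two parties. On that wording, the medical monitor alone cannot restore an exempted event.

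At stake is the count behind every escalate, stay or de-escalate decision, and behind DLT as a primary endpoint (SAP 5.1.1, reported under SAP 5.6.2.1).

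**Working it through.** **Inputs from the documents.** Target 25%, equivalence interval 20% to 30%, cohorts of 2 (Protocol Table 1). Beta(1, 1) prior, ten intervals of width 10%, and a 95% cut-off for an unacceptable dose (Protocol 9.7.4.1). The MTD estimate uses a "non-informative beta prior distribution Beta (0.005, 0.005) will be used to determine the estimate of DLT rates at each dose", followed by isotonic smoothing.

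**Inputs that are assumptions.** The share q of all DLTs that is exempted, taken from 0 to 40%; the documents give no figure.

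**Step 1: reproduce Table 1.** With y DLTs in n subjects the posterior is Beta(1+y, 1+n−y), and the decision follows the interval with the largest mass. Four cells:

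| y/n | Posterior | Largest interval (mass) | 20–30% mass | Decision |
|---|---|---|---|---|
| 0/2 | Beta(1, 3) | 0–10% (0.271) | 0.169 | E |
| 1/2 | Beta(2, 2) | 40–50% and 50–60% (0.148 each) | 0.112 | D |
| 1/6 | Beta(2, 6) | 10–20% (0.274) | 0.247 | E |
| 2/6 | Beta(3, 5) | 30–40% (0.227) | 0.205 | D |

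All 36 cells checked agree with Table 1 (n = 2 to 12; counts 0 to 5 and the first of the six-or-more row). The numerical rule is sound; the issue is only what enters the count.

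**Step 2: remove one event.** The decision changes as follows: 1/2 to 0/2, D to E; 2/4 to 1/4, D to S; 2/6 to 1/6, D to E; 3/8 to 2/8, D to S; 3/12 to 2/12, S to E. Not every removal matters: 1/6 to 0/6 stays E and 3/6 to 2/6 stays D.

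**Step 3: what a counted 25% would mean.** Counted rate = true rate × (1 − q), so true rate = 0.25/(1 − q).

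| q | True rate when 25% is counted |
|---|---|
| 0 | 25.0% |
| 10% | 0.25/0.9 = 27.8% |
| 20% | 0.25/0.8 = 31.3% |
| 30% | 0.25/0.7 = 35.7% |
| 40% | 0.25/0.6 = 41.7% |

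**Step 4: chance of escalating after the first 2 subjects.** This is (1 − p(1 − q))². At an assumed true rate p = 35%: q = 0 gives 0.65² = 42%; q = 10%, 0.685² = 47%; q = 20%, 0.72² = 52%; q = 40%, 0.79² = 62%.

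**Step 5: why the low end is more plausible.** q refers to all DLTs, but only one criterion can be exempted. If half of DLTs fell under it and 20% of those were exempted (both assumed), q = 0.5 × 0.2 = 10%. The equivalent true rate is then 27.8%, still inside the 20% to 30% interval.

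**Step 6: illustration for the MTD.** Trials were simulated at 4,000 per value of q, with 36 subjects in cohorts of 2, the Protocol 9.7.4.1 rules, and ten doses with assumed true rates of 2, 3, 5, 8, 12, 18, 25, 35, 45 and 55%. The chance that the selected MTD has a true rate above 30% is 21.5% at q = 0, 40.2% at q = 20% and 65.0% at q = 40%. This describes the design if run to an MTD, not what happened in this trial.

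**The case against.** The strongest reply is that the clause is narrow and the plan has other protections.

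- **Scope.** A reader might infer that any Grade ≥3 event can be exempted. The text does not support that. The clause sits under one criterion. The separate criteria for laboratory findings, hematologic toxicity, Cycle 2 delay, death, hepatic metastases and Hy's law do not contain it, and an event exempted under the first criterion may still count under one of them.
- **Both conditions.** The event must be judged neither dose limiting nor dose related, so the circularity touches only one of two conditions.
- **Direction.** A reader might infer that judgement can only remove DLTs. Two routes add them. What is unequal is who must concur.
- **Definition.** The 25% target can be read as the rate of DLTs as the protocol defines them, exemption included. The weakness is then a subjective definition that may vary between investigators.
- **Safeguards.** A reader might infer that an exempted event leaves escalation unrestricted. Table 2 limits the step to a new dose level to about 10% to 30% after any related Grade ≥3 event, DLT or not. Dose assignment follows consultation between investigators and sponsors, and RP2D selection (9.1.1.3) weighs related toxicity not classed as dose limiting.
- **Existing outputs.** SAP 5.6.2 already lists DLTs and Grade ≥3 AEs.

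The first three points stand and set the scope. The definition point changes how the weakness is described but does not remove it. The safeguards soften the consequence only. Table 2 governs step size, does not turn E into S or D, and does not apply when moving to a dose already tested. Consultation starts from the DLT count after exemptions. RP2D selection is capped by an MTD estimated from that same count. The listings are not specified to show which events were exempted, or why.

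**Conclusion.** The concern holds for clinically significant nonhematologic Grade ≥3 events only. There, an investigator acting alone can exempt a related event, while judgement-based additions need a second party. Each use can only lower the count under that criterion, and one event can change the Table 1 decision.

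That DLTs actually are undercounted is a tempting conclusion, but the documents do not support it: they give no exemption frequency, and at q = 0 there is no bias. If 10% to 40% of all DLTs were exempted, a counted 25% would correspond to a true rate of about 28% to 42%. This assumes that exemptions thin all DLTs evenly, and the likely position is toward the low end.

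SAP section 7 states that the MTD was not determined, and SAP 3.2.2 that no expansion subjects will be enrolled. No MTD estimate or expansion dose is therefore affected. What remains is the escalation decisions and the DLT rate reported by dose. This is a cheap improvement in how the count is governed and reported, not an error in the dose-finding rule.

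**What to change.** Leave the clinical criteria unchanged.

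1. In Protocol 9.1.1.2 and the synopsis, require documented concurrence of the existing Study Safety Committee, with reasons, for each use of the exemption before the dose decision.
2. In the Grade ≥3 AE listing of SAP 5.6.2.2, flag each related event that was exempted.
3. Under SAP 5.6.2.1, report the DLT count and the resulting Table 1 decision by dose level twice: as classified, and with exempted events counted as DLTs.

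Items 2 and 3 concern reporting only, so they remain useful without an MTD. The cost is one sentence in the protocol, one flag, one extra tabulation and one committee entry per exempted event.

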#### DOSE ADJUSTMENTS

E7766 Dose Adjustments

• In the Dose Escalation part, dose adjustments may be allowed at the discretion of the

Eisai Confidential Page 16 of 138

investigator after discussion with the sponsors. Subject may be allowed to continue study drug at a reduced dose, if this is judged to be in their best interest. E7766 dose reductions and interruptions should be carried out as outlined in "E7766 Dose Reduction and Interruption Instructions."

#### Guidelines for dose adjustments after Cycle 1

E7766 dose reduction and interruption for subjects who experience therapy-related toxicity (as assessed by the investigator) will be in accordance with the dose modification guidelines described in the "E7766 Dose Reduction and Interruption Instructions."

• Subjects who experience toxicities that could have been qualified as DLTs may, at the discretion of the investigator and after discussion with the sponsor, be allowed to continue study drug at a reduced dose according to these dose modification guidelines, if this is judged to be in their best interest.

For subjects who require dose interruption due to E7766-related toxicity in Cycle 2 or beyond, the treatment may re-start once the toxicity has been resolved to Grade ≤1 or the baseline value according to the Dose Reduction and Interruption Instructions in the table below."

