## 9.4.1.2 Dose Adjustments

### E7766 Dose Adjustments

In the Dose Escalation part, dose adjustments may be allowed at the discretion of the investigator after discussion with the sponsors. Subject may be allowed to continue study drug at a reduced dose, if this is judged to be in their best interest. E7766 dose reductions and interruptions should be carried out as outlined in Table 4.

## Guidelines for dose adjustments after Cycle 1

E7766 dose reduction and interruption for subjects who experience therapy-related toxicity (as assessed by the investigator) will be in accordance with the dose modification guidelines described in Table 4.

• Subjects who experience toxicities that could have been qualified as DLTs may, at the discretion of the investigator and after discussion with the sponsors, be allowed to continue study drug at a reduced dose according to these dose modification guidelines, if this is judged to be in their best interest.

For subjects who require dose interruption due to E7766-related toxicity in Cycle 2 or beyond, the treatment may re-start once the toxicity has been resolved to Grade  $\leq 1$  or baseline according to the dose reduction and interruption instructions in Table 4.

Table 4 E7766 Dose Reduction and Interruption Instructions

E7766-Related Toxicity a	During Therapy	Approximate Dose Adjustment		
Grade 1				
	Continue E7766 treatment.			
All occurrences	If CRS, then interrupt E7766	Maintain dose level.		
	until Grade 0.			
	Grade 2 b			
	Interrupt E7766 until resolved to			
1st occurrence	Grade ≤1 or baseline.	Maintain dose level.		
1st occurrence	If CRS, then interrupt E7766	If CRS, consider dose reduction.		
	until Grade 0°.			
	Interrupt E7766 until resolved to	Consider reduction by 1 dose level of starting		
2nd occurrence	Grade ≤1 or baseline.	dose, if dose delayed.		
(same toxicity)	If CRS, then interrupt E7766	If CRS, then consider further dose reduction.		
	until Grade 0°.			
3rd occurrence	Interrupt E7766 until resolved to	Reduce by 1 or 2 dose levels of starting dose,		
	Grade $\leq 1$ or baseline c .			
(same toxicity)	If CRS, then discontinue E7766.	if appropriate.		
4th occurrence	Interrupt E7766 until resolved to	Digayag with anangara		
(same toxicity)	Grade $\leq 1$ or baseline c .	Discuss with sponsors.		
Grade 3 b				
1st occurrence	Interrupt E7766 until resolved to	Reduce by 1 dose level of starting dose		

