### 9.4.1.4 Management of Cytokine Release Storm

Cytokine release storm (CRS) has been identified as a potential safety risk in immunotherapies, especially drugs that act as agonists for immune activation. Guidance for identification and management is provided in Table 5. IL-6 will be assessed by the site as clinically indicated. For E7766 dose adjustments and interruptions for the management of CRS, refer to Table 4.

Table 5 Management of Cytokine Release Storm and Organ Toxicity

CRS Grade	Sign/Symptom	Management
(CTCAE)		
Grade 1	Fever or Grade 1 organ toxicity	
 
Acetaminophen and hypothermia blanket as needed for fever
 
Ibuprofen if fever is not controlled with above; use with caution or avoid if thrombocytopenic
 
Assess for infection with blood and urine cultures, and chest x-ray
 
Consider antibiotics and filgrastim (if neutropenic)
 
IV fluids as needed
 
Symptomatic management of constitutional symptoms and organ toxicities
 
Consider IL-6 antagonist for persistent (greater than 3 days) or refractory fever
 

Grade 2	Hypotension	
 
IV fluid bolus of 500 – 1,000 mL normal saline; repeat as necessary to maintain SBP greater than 90 mmHg
 
Consider IL-6 antagonist¹ for hypotension refractory to fluid boluses
 
If hypotension persists after two fluid boluses and IL-6 antagonist¹, start vasopressors, transfer patient to ICU, and obtain ECHO
 
In patients at high-risk for severe CRS², if hypotension persists after IL-6 antagonist¹, if there are signs of hypoperfusion³ or if there is rapid deterioration in the opinion of the clinician, may use dexamethasone 10 mg IV every 6 hours
 
Manage fever and constitutional symptoms as in Grade 1 CRS
 

	Hypoxia  Grade 2 organ toxicity	
 
Use supplemental oxygen as needed
 
Use IL-6 antagonist with or without corticosteroids as in hypotension
 
Manage fever and constitutional symptoms as in Grade 1 CRS
 
Manage organ toxicity as per standard guidelines
 
Use IL-6 antagonist with or without corticosteroids as in hypotension
 
Manage fever and constitutional symptoms as in Grade 1 CRS
 

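### Section 9.1.1.2 and the synopsis permit a reduced dose after any resolved DLT, with no exception for the events at which Table 4 requires discontinuation

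*Protocol*

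**What the plan says.** Protocol 9.1.1.2 ends with a rule for subjects who have had a DLT: "A subject experiencing a DLT may continue treatment at a reduced dose if the DLT has resolved", on the further condition that the investigator considers the subject to be benefiting. It names one stop: "In case of recurrence of the DLT at a lower dose, E7766 treatment should be discontinued". The synopsis repeats both sentences after its DLT definition. Neither place sets a grade limit, excepts CRS or refers to Table 4.

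Table 4 (9.4.1.2) works by grade. A first Grade 3 event leads to interruption and a one-level reduction, unless it is CRS, in which case E7766 is stopped. The Grade 4 row also stops E7766. Two footnotes narrow the table. Footnote a removes anemia, lymphocytopenia, alopecia and neutropenia without symptoms. Footnote d has Grade 4 laboratory findings that are not thought life-threatening handled as Grade 3. The synopsis version of the table carries the same Grade 3 CRS rule.

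Two other passages bear on which rule governs. For Dose Escalation, 9.4.1.2 says "In the Dose Escalation part, dose adjustments may be allowed at the discretion of the investigator after discussion with the sponsors" and then "E7766 dose reductions and interruptions should be carried out as outlined in Table 4". The synopsis has the matching sentence, "E7766 dose reductions and interruptions should be carried out as outlined in", followed by the name of its own table. Section 9.4.1.4 says "For E7766 dose adjustments and interruptions for the management of CRS, refer to Table 4", and the synopsis does the same for its table.

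**The concern.** The DLT list in 9.1.1.2 includes "Clinically significant nonhematologic toxicity ≥ Grade 3", with listed exceptions, and "Grade 4 thrombocytopenia, or Grade 3 thrombocytopenia with hemorrhage". A related Grade 3 CRS or Grade 4 event in Cycle 1 can therefore be a DLT. For that subject the DLT paragraph, read alone, lets dosing resume at a lower dose once the event has resolved, while Table 4 says to stop.

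This is a first-in-human study of a drug for which the protocol itself names CRS as a potential risk. A site working from the DLT section could re-dose a subject whom a site working from Table 4 would take off treatment. Participant safety and uniform dosing are at stake.

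**Working it through.** No arithmetic applies; the check compares the two rules event by event. In each of the first five rows the event is taken to be a Cycle 1 DLT that has resolved, in a subject judged to be benefiting.

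| Event | DLT paragraph (9.1.1.2) | Table 4 (9.4.1.2) | Result |
|---|---|---|---|
| First Grade 3 CRS | Reduced dose permitted | Discontinue | Opposed |
| Grade 4, nonhematologic, not a laboratory finding, not CRS | Reduced dose permitted | Discontinue | Opposed |
| Grade 4 thrombocytopenia judged life-threatening | Reduced dose permitted | Discontinue (not in footnote a; outside footnote d) | Opposed |
| Grade 4 laboratory finding judged not life-threatening | Reduced dose permitted | Handled as Grade 3: one-level reduction | Consistent |
| Grade 4 neutropenia without symptoms | Reduced dose permitted | Outside the table (footnote a) | Consistent |
| Same non-CRS Grade 3 DLT again, at a lower dose | Discontinue | Reduce by two levels | Opposed, with the DLT paragraph stricter |

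On first occurrence the disagreement is confined to two Table 4 entries: Grade 3 CRS, and Grade 4 outside footnotes a and d.

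The next question is whether other text settles these cases.

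- **CRS.** Section 9.4.1.4 and its synopsis counterpart send CRS dose adjustments to the table with no cycle limit. Table 4 is clearly the better reading.
- **Grade 4 other than CRS.** Section 9.4.1.4 does not apply. The Dose Escalation paragraph of 9.4.1.2 stands ahead of the after-Cycle-1 guidelines and sends reductions and interruptions to Table 4 after sponsor discussion. It favors Table 4, but it does not mention discontinuation and does not say that the table's stops override 9.1.1.2. It can be read as governing how to reduce, not whether the subject may continue.
- **Contrast within 9.4.1.2.** The bullet on DLT-type toxicities after Cycle 1 ties continued dosing to the dose-modification guidelines. The DLT paragraph in 9.1.1.2 has no such tie, and a reader could take the difference as intended.

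**Effect on dose finding.** Under Protocol 9.7.1.2 and SAP 5.2.1, a subject with a Cycle 1 DLT belongs to the DLT Analysis Set whether or not dosing resumes. The DLT count, the mTPI-2 decision and the MTD estimate are therefore the same under either rule.

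**The case against.** The strongest reply is that the protocol, read as a whole, already answers the question. DLTs are a Dose Escalation concept, and 9.4.1.2 routes every Dose Escalation reduction through Table 4. That table outlines no reduction for Grade 4 outside its footnotes, only discontinuation. The DLT paragraph is permissive and the table directive, so stopping satisfies both. A DLT must also resolve, and benefit must be judged, before re-dosing. The reduced dose would then usually fall in Cycle 2 or later, where the after-Cycle-1 guidelines apply Table 4 expressly. On this view only a cross-reference is missing.

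Much of this stands. A reader might infer that the protocol endorses re-dosing after Grade 3 CRS, or that nothing connects the DLT paragraph to Table 4. Sections 9.4.1.2 and 9.4.1.4 do not support either inference. Re-dosing within the same cycle is also unlikely: sponsor discussion applies, and the first scheduled on-study scan comes at about 6 weeks for solid tumors or Week 9 for lymphoma. Benefit could be judged sooner, since Table 7 has the injected lesion measured on each dosing day.

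The reply does not remove the contradiction. It reaches the right answer by inference across sections, whereas the DLT paragraph speaks directly to the subject in question and reads as complete in itself. For Grade 4 events other than CRS, the inference rests on sentences that do not mention discontinuation.

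**Conclusion.** The point holds in limited form. The DLT paragraph contradicts Table 4 on its face for a first Grade 3 CRS and for Grade 4 outside footnotes a and d. Table 4 is the better reading, clearly for CRS and less securely for other Grade 4 DLTs. The text should be corrected, because it concerns re-dosing after severe toxicity in a first-in-human study.

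The size cannot be given: the documents do not state what share of DLTs is expected to be Grade 3 CRS or Grade 4. The conclusion assumes that the event is classed as a DLT; a Grade 3 CRS judged neither dose limiting nor dose related would not be.

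Three further inferences are not supported:

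- **That the DLT paragraph is looser throughout.** On recurrence it is stricter than Table 4.
- **That the MTD would be biased.** DLT classification does not depend on later dosing, and SAP Section 7 says that no MTD was determined.
- **That the synopsis shows the same Grade 4 conflict.** As extracted, its table has footnote d but no Grade 4 row, so the Grade 4 rule can be verified only in Table 4 of the body. The gap may be an extraction loss and is not counted against the plan.

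The SAP also records that escalation ended early and that no expansion subjects will be enrolled. This limits future exposure. It does not reconcile the rules, since treatment may continue past the data cutoff (SAP Section 5) and, after discussion with the sponsors, past study termination (Protocol 9.1.3.3).

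**What to change.** In 9.1.1.2, add to the permission: *except where Table 4 requires discontinuation (eg, Grade 3 CRS; Grade 4 subject to footnotes a and d)*. In the synopsis, add the same clause but name its own table, *E7766 Dose Reduction and Interruption Instructions*.

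Leave the requirement that the DLT has resolved and the stop on recurrence as they are. Table 4 then only adds stops, and its two-level reduction for a second Grade 3 event does not displace the stricter recurrence rule. The cost is one clause in two places, with no new data or subjects.
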